3.3 Informed Consent Process

All participants must be provided a consent form describing the study with sufficient information for participants to make an informed decision regarding their participation. Participants must sign the IRB-approved informed consent prior to participation in any study specific procedure. The participant must receive a copy of the signed and dated consent document. The original signed copy of the consent document must be retained in the medical record or research file.

3.4 Randomization Procedures

We will use a blocked randomization design. Approximately 60 subjects will be randomized in a 4:1 ratio to the intervention arm (VLNT + BioBridge): control arm (VLNT alone). Randomization will be done within blocks (of size 5) so that the balance between treatments is preserved throughout the trial, where A = VLNT/Biobridge and B = VLNT alone.

The order in which these blocks will be assigned to the enrolled subjects will be prospectively, independently determined through a random number generator function.

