2.4 Study Design

For clinicaltrials.gov and Stanford Clinical Trials Directory compliance

- Primary purpose of the protocol:
 - **Treatment:** protocol designed to evaluate one or more interventions for treating a disease, syndrome or condition
- Interventional model:
 - **Parallel:** one of two groups in parallel for duration of study.
- State the number of intervention arms
 - **Two arms**
- State whether the study will be masked (at least one party is unaware of the treatment)
 - **Open:** no masking is used
- State whether the study is randomized.
 - **Randomized**
- Primary outcome or outcome that the protocol is designed to evaluate:
 - **Efficacy**

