SutureEase device will be used to tunnel five 15 cm long Fibralign BioBridge Collagen Matrix individually in the subcutaneous tissue from the lymph node flap down to the mid forearm. 3 additional 15 cm long BioBridge Collagen Matrix are similarly tunneled proximally pass the shoulder toward the neck and two 15 cm long BioBridge Collagen Matrix are tunneled to the axilla. Prior to implantation, the BioBridge is moistened in saline, to facilitate gliding in tissue. Once this is completed, the skin flaps are redraped over the fascial-lymph node flap and closed with interrupted 3-0 Vicryl sutures for the dermis and 4-0 Monocryl running subcuticular stitch for the skin. The total length of time spent on placement of the Biobridges is about 45 minutes.

At the end of the procedure, Doppler signal from the flap, correct sponge and needle counts will be verified. Minimal blood loss is expected. The patient will be awakened; extubated; and transferred to the recovery room.

Standard PACU recovery: 1 to 1.5 hrs.

Hospitalization: 2 to 3 days, managed postoperative in accordance to the institution standardized free flap protocol.

Post-op instructions (specific to this procedure-VLNT): patients are instructed to keep their surgical arm elevated x 3 weeks at level of heart or above. Otherwise, patient may ambulate, eat and resume normal light activities that does not require use of treated arm. Patients will be instructed to not wear compression garments for 3 weeks post-operative.

Participants will be given consent form and contact information to take home for their consideration. Samples (skin punch biopsy and blood) may be retained for future research use if patient has given consent (in ICF). Pre-treatment and post-treatment photographs will be taken.

Study Visits

There are 3 screening visits.

S1: after obtaining written consent, medical history, symptoms, current medications, and allergies will be reviewed, height/weight/VS, physical exam by PI will be conducted, limb measurements performed (volume, BIS, caliper), and LymQoL survey completed.

S2: VS, weight, medication and allergy review, measurements; if measurements are consistent, will proceed to skin punch biopsy (optional for control group); research labs will be drawn. No compression garment wear x 10 days.

S3: VS, weight, medication and allergy review, measurements, stitch removal, LSG. Patients resume wearing compression; after 3 weeks, eligible to proceed with surgery.

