5.2 Availability

The investigational device will be provided by Fibralign Corporation. It will be ordered specifically for each subject and will be shipped directly to the PI/Co-PI.

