12. STATISTICAL CONSIDERATIONS

12.1 Statistical Design

This study is open-label due to visibly apparent differences between the recipients of the surgery.

Primary Endpoint:

The primary outcome is the post-surgical % change in excess limb volume, measured at 12 months, following the surgical procedure.

Secondary Endpoint:

For secondary endpoint, the mean response of the intervention group will be compared to the control group, for change in measurement of dermal thickness, as measured by caliper skin fold thickness, from screening evaluations to Month 12.

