12.6 Sample Size

12.6.1 Accrual estimates

[name] directs a national referral center for lymphatic disorders and approximately 600 new patients with clinically significant lymphedema are seen in on a yearly basis. Some of these patients are referred from the breast clinic but majority comes from local and regional physician offices. [name] performs 15 to 19 vascularized lymph node transfers yearly (of subjects who meet the eligibility criteria). We expect to be able to accrue subjects to this study within 48 months. Once study has been approved and is enrolling, in order to facilitate enrollment in the allotted time frame, we plan to add 3 subsites in order to meet accrual goal.

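### Section 3.4 publishes a fixed block size of 5 (one control per block) in an open-label trial with no stated concealment; in the upper-end case 44% of assignments could be known in advance, though best-guess accuracy rises only from 80% to 84%.

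*Combined protocol and SAP*

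**What the plan says.** Section 3.4 sets 4:1 allocation of about 60 subjects and gives a single block size with its reason: "Randomization will be done within blocks (of size 5) so that the balance between treatments is preserved throughout the trial". It adds that the order of the blocks is "prospectively, independently determined through a random number generator function". Section 12.1.1 repeats blocked 4:1 randomization of sixty subjects and adds nothing on method.

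Section 2.4 records that "no masking is used", and section 12.1 says: "This study is open-label due to visibly apparent differences between the recipients of the surgery". On the device, section 5.2 states: "It will be ordered specifically for each subject and will be shipped directly to the PI/Co-PI". At the first screening visit (section 4, Study Visits, S1), "physical exam by PI will be conducted". On recruitment, section 12.6.1 says a clinician at the lead center "performs 15 to 19 vascularized lymph node transfers yearly" and that "we plan to add 3 subsites in order to meet accrual goal".

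The sections available for review name no list holder, central system, envelopes or varying block sizes. They give no point at which an assignment is released, and do not say whether the sites share one list or hold one each.

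**The concern.** With one control per block of 5, the rest of the block is certain to be BioBridge once that control has been used. If the first four are BioBridge, the fifth is certain to be control. Anyone who has read section 3.4 and can count past assignments can work this out.

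Knowledge of past assignments is plausible at the lead site. The surgery is unmasked, devices are ordered per subject and sent to the investigators, and the principal investigator examines candidates. Most entry criteria are numeric, but surgical eligibility (3.1.5) and the general investigator-opinion exclusion (3.2.21) leave some discretion. Sections 4 and 9 also make the S2 skin biopsy optional for controls. This leaves open whether the arm is already known at S2, when the volume and L-Dex criteria are still being measured.

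At stake is comparability of the arms. With only 12 controls, a few steered enrolments can move the control mean, and adjustment for measured baseline factors would remove only part of such bias. The primary model in section 12.4 has no baseline covariate.

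**Working it through.** **Plan's own figure.** The documents give no predictability figure. Their only design calculation is in section 12.6.2: 48 vs 12, SD 19%, alpha 0.05, power 0.9, detectable difference 20%. The standard error is 19 × √(1/48 + 1/12) = 6.13, and 6.13 × (1.960 + 1.282) = 19.9, so it reproduces. Power for a difference of 20 is 0.90 by the normal approximation and 0.894 by the t-test. Block size does not enter.

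**Inputs.** Block size 5, ratio 4:1, 60 subjects, hence 12 blocks (sections 3.4 and 12.1.1). Assumption: the control is equally likely in each of the five positions.

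**One list, block size and all earlier assignments known.**
- Certain BioBridge per block: (4 + 3 + 2 + 1 + 0)/5 = 2.0.
- Certain control per block: 1/5 = 0.2.
- Share certain: 2.2/5 = 44%. Over 12 blocks: 24.0 + 2.4 = 26.4 of 60.
- Best guess correct, positions 1 to 5: 0.8; 0.8 × 0.75 + 0.2 = 0.8; 0.6 × 2/3 + 0.4 = 0.8; 0.4 × 0.5 + 0.6 = 0.8; 1. The mean is 4.2/5 = 84%, against 80% for always guessing BioBridge.

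**Other list structures** (subjects spread at random and equally over sites).
- Separate lists at four sites: about 41% by simulation. It is below 44% because some blocks stay unfinished and the last slots of a block are the most predictable.
- One shared list over S sites, own assignments and sequence number visible: (2.0/S + 0.2/S⁴)/5, which is 20% for two sites and 10% for four.
- One shared list, sequence number hidden: near 0%. For example, after a site's own history of BioBridge, BioBridge, control, the chance that its next assignment is control is still 8% (two sites) or 12% (four).

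**Illustration of bias, one visible list.** The documents give no steering size, so assume that an enroller can shift expected outcome by s = 1 to 5 points: up in certain-BioBridge slots, down where the chance of control is at least 1/3. Per block, the downward-steered slots hold on average 0.6 BioBridge and 0.6 control subjects. The BioBridge mean moves (2.0 − 0.6)s/4 = 0.35s and the control mean −0.6s. The difference is 0.95s, or 0.95 to 4.75 points against the 20-point target. Steering only certain slots gives 0.5s + 0.2s = 0.7s, or 0.7 to 3.5 points. These are near-worst-case figures.

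**Random blocks of 5 and 10 ending at 60** (simulated lists; enroller assumed to know the two sizes and all earlier assignments).
- Certain: about 13.5% (8.1 of 60: 7.5 BioBridge, 0.6 control). Best guess: about 82%. Under the same assumed steering, 0.49 to 2.45 points.
- If 20 subjects are already randomized, the remaining 40 have 15.1% certain: (20 × 0.44 + 40 × 0.151)/60 = about 25% for the whole trial. If 40 are already randomized, the remaining 20 have 18.9%: (40 × 0.44 + 20 × 0.189)/60 = about 36%.

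**The case against.** The strongest reply is that 44% is the upper-end case and overstates the information gained. It needs one list, a known block size and full knowledge of earlier assignments. Of the 26.4 certain slots, 24 are BioBridge, already the likely arm, and only 2.4 of 12 controls are foreseeable with certainty. Three subsites are planned, and local knowledge of a shared list is much weaker. Room to steer is narrow: entry rests mainly on measured criteria over three screening visits, and 15 to 19 eligible transfers a year is only 60 to 76 over 48 months, so the lead site alone has few patients to spare. Small blocks also have a stated purpose, balance throughout the trial, which matters with 12 controls. All of this stands and limits the size of the point.

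The plan's reference to an independently determined random order is only a partial defence. It describes how the sequence is generated, not who is kept from it. The blinded reviewers and caliper assessor in section 10 protect outcome assessment, not enrolment.

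A reader might go further and infer that allocation was not concealed in practice, that 44% of assignments were in fact foreseen, or that the comparison is biased. The documents support none of these. They are silent on concealment, some pages were not available for review, and nothing shows that anyone used the block structure.

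**Conclusion.** The point holds in a limited form. As written, section 3.4 makes part of the sequence predictable in an open-label trial and states no safeguard. The certain share runs from near 0% to 44%, depending on list structure and what enrollers can see. The documents settle neither. Even at 44%, best-guess accuracy gains only 4 percentage points over always guessing BioBridge.

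The size of any bias cannot be derived from the documents. The 0.95 to 4.75 points above rest on an assumed steering size, and the real figure is probably much smaller. The change is worth making because it removes most of an avoidable opportunity at modest cost, in a trial where the control mean rests on 12 subjects. A missing description of concealment would alone be a gap in detail; the published fixed block size is what can be improved in method.

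**What to change.** For subjects not yet randomized:

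1. State in section 3.4 that one list is shared across the lead site and the subsites. The scheme below needs this, since a list ending at exactly 60 presumes a single list.
2. Release each assignment only after eligibility is confirmed and recorded, without showing the list's sequence number. Say how this fits with the S2 biopsy being optional for controls.
3. Move the block size from section 3.4 to a restricted document held by someone not involved in enrolment.
4. Finish any open block of 5, then use randomly ordered blocks of 5 and 10, all 4:1, generated to end on a complete block at 60 with 12 controls.

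**Cost.** An amendment with IRB approval before implementation (section 11.1) and a regenerated list. Sample size, ratio, the 12 controls and power do not change. Balance over time loosens. The longest possible BioBridge run rises from 4 + 4 = 8 to 8 + 8 = 16; at 60/48 = 1.25 subjects a month that is 6.4 against 12.8 months. The chance of a run over 8 is about 48%, of 12 or more about 7%, and of 16 under 0.1%. If accrual stops mid-block, controls could be up to 8/5 = 1.6 short of 4:1, rather than 4/5 = 0.8. If the sponsor judges that balance cost too high, items 1 to 3 are still worth making alone.

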On the strength of our preclinical findings, we propose a prospective clinical investigation of the impact of BioBridge as an adjunct to VLNT. VLNT is an increasingly practiced surgical intervention for limb lymphedema, despite the fact that the documented success rate of the current procedure is not optimal. Of published studies reporting limb volume outcomes after VLNT, volume changes range from an increase of 13% to a decrease of 64% (from presurgical volume).³⁴ Animal studies suggest that surgical failure may be due to inadequate lymphatic vascular engraftment of the transplanted node.⁴⁸ VLNT with placement of the BioBridge scaffold is intended to provide lymphatic soft tissue support that is needed for effective lymphatic revascularization of the transplanted node. It is hoped to demonstrate that the BioBridge improves upon the less-than-optimal success rate of the currently practiced surgery.

by facilitating the lymphatic connections to the transplanted node that are crucial to its viability and function.³⁴ The proposed study will evaluate the clinical efficacy of adjunctive BioBridge use in VLNT. We hypothesize that BioBridge will have the capacity to substantially improve the efficacy of VLNT, providing the stable and optimally predictable outcomes that are currently lacking for the unaided procedure. We have therefore designed a novel approach to treatment that directly addresses a component of the underlying cause and may be more effective as a treatment strategy.

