Xylocaine with epinephrine is used as a local anesthetic. Potential risks include: feeling anxious; shaky; dizzy; restless; or depressed; drowsiness; vomiting; ringing in your ears; blurred vision; confusion; twitching; seizure (convulsions); fast heart rate; rapid breathing; feeling hot or cold; weak or shallow breathing; slow heart rate; weak pulse; or feeling like you might pass out. Less serious side effects include: mild bruising; redness; itching; or swelling where the medication was injected; mild dizziness; nausea; numbness in places where the medicine is accidentally applied.

For biopsy, cephalexin (unless allergic to this antibiotic):

Cephalexin is an antibiotic. Possible adverse effects include the following:

- Central nervous system: Agitation, confusion, dizziness, fatigue, hallucinations, headache
- Dermatologic: allergic swelling, severe rash, Stevens-Johnson syndrome, toxic epidermal necrolysis, hives
- Gastrointestinal: Abdominal pain, diarrhea, stomach burning, gastritis, nausea , colitis, vomiting
- Genitourinary: Genital itching, genital thrush, vaginitis, vaginal discharge
- Hematologic: elevated white blood cell counts
- Hepatic: abnormal liver function, jaundice , transient hepatitis
- Neuromuscular & skeletal: joint aching and swelling, joint disorder
- Renal: kidney inflammation
- Miscellaneous: Allergic reactions

Phlebotomy (SOC and research):

Risks of blood samples being drawn include: pain; bruising; bleeding; inflammation; infection; temporary redness of the skin where the injection is given; and light headedness. Care will be taken to avoid these difficulties.

Bioimpedance spectroscopy (BIS) (research):

Placement of and/or removing the pads may cause skin irritation; BIS analysis is painless.

Calipers (research):

The calipers may cause some discomfort due to the pinching of the skin.

Stanford Experience

[name] has performed more than 100 cases of VLNT over the last 5 years. The average volume reduction is 55 to 65%. There has not been any flap loss. There is < 5% post-operative infection; < 5% wound dehiscence; 2% of seroma; 2% of hematoma; 1% post-operative deep vein thrombosis (DVT). There have had no major complications. To date, there has been no incidence of donor site lymphedema. In general, this is a well-tolerated operation. The positive outcome is, in part, dependent upon patient compliance with postoperative instructions.

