12.1.1 Randomization

A blocked randomization design will be used for randomization. Sixty subjects will be randomized in a 4:1 ratio to the intervention arm (VLNT + BioBridge) or control arm (VLNT alone).

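### Three subsites are planned, but neither the randomization nor the primary model takes account of site, so chance site imbalance among 12 controls would go uncorrected and could cost power

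*Combined protocol and SAP*

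**What the plan says.** Section 3.4 states: "Approximately 60 subjects will be randomized in a 4:1 ratio to the intervention arm (VLNT + BioBridge): control arm (VLNT alone"). Blocks have size 5, so each holds one control, and "The order in which these blocks will be assigned to the enrolled subjects will be prospectively, independently determined through a random number generator function". The purpose given is that "Randomization will be done within blocks (of size 5) so that the balance between treatments is preserved throughout the trial". Section 12.1.1 adds only that "A blocked randomization design will be used for randomization". Neither section names site, surgeon or any other stratum.

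Section 12.6.1 reports that one operator "performs 15 to 19 vascularized lymph node transfers yearly (of subjects who meet the eligibility criteria"), and that, to enrol in time, "we plan to add 3 subsites in order to meet accrual goal". It does not say who will operate at the subsites or how many patients each will contribute.

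The primary model in section 12.4 contains a subject random intercept, treatment, month, and treatment-by-month terms. It has no site or surgeon term, and no other section deals with site. Section 12.3 plans no descriptive analysis, so no specified output would show how the controls are spread across sites.

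On VLNT results, section 4.1 reports for the lead operator: "The average volume reduction is 55 to 65" per cent. Section 12.6.2 uses a 51% reduction with SD 19% from a published study. Section 2.3 says that across published studies "volume changes range from an increase of 13% to a decrease of 64% (from presurgical volume").

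**The concern.** VLNT is the background procedure in the BioBridge arm and the whole treatment in the control arm. Anything about a site that affects its result, such as operator, donor-site choice or aftercare, affects the endpoint in both arms. Blocking over calendar time keeps the 4:1 ratio but does not keep the arms alike in site mix. With 12 controls over four sites, a shift of two or three controls changes that mix noticeably.

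The subject random intercept does not solve this. It absorbs site differences into between-subject variance, but treatment is compared between subjects, so a chance difference in site mix stays in the estimate. At stake are the precision of the month-12 comparison and the stated 90% power, which has no between-site component.

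**Working it through.** **Plan's own figure.** Inputs from section 12.6.2: 48 v 12, SD 19, alpha 0.05 (two-sided, as in the section 12.4 hypothesis), power 0.90.
- SE = 19 × √(1/48 + 1/12) = 6.13.
- Detectable difference = 6.13 × (1.960 + 1.282) = 19.9 points; 20.2 with the t distribution.
- Power at 20 points = 0.903 (normal) or 0.894 (t).

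The plan's ±20% is reproduced.

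**Are subsites needed?** 15 to 19 eligible cases a year over 48 months is 60 to 76. Enrolling 60 from one operator would need 60/76 = 79% to 60/60 = 100% of them.

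**Assumptions.** The documents give no site shares and no between-site difference. I assume one list for all sites, a 30/10/10/10 split, and lead-v-subsite differences D of 10, 20 and 30 points.

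**Chance imbalance.** If k of the 12 controls are at the lead site, the gap in lead-site share between arms is (30 − k)/48 − k/12 = 0.625 − k × 5/48. Each control away from k = 6 therefore adds 5/48 = 0.104. Treating k as a draw of 12 from 60 with 30 at the lead site:
- SD of k = √(12 × 0.5 × 0.5 × 48/59) = 1.56, so the SD of the gap = 1.56 × 0.104 = 0.16.
- P(off by 1 or more) = 0.75 and P(off by 2 or more) = 0.33, so the median absolute gap is 0.104.
- P(off by 3 or more) = 0.10, so the 90th percentile is 3 × 0.104 = 0.31.

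Simulating the blocks of 5 gives the same values. With four equal sites the SD is 0.14 and the 90th percentile 0.21.

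**Shift in the realised estimate** = gap × D. At D = 20 it is 0.104 × 20 = 2.1 points at the median and 0.31 × 20 = 6.2 points at the 90th percentile, against an SE of 6.1.

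**Power.** With half the patients at the lead site and no site term, the outcome SD becomes √(19² + D² × 0.25), and SE = SD × 0.3227. The simulated column analyses the month-12 value with a t test.

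| D | SD | SE | Power, normal approximation | Power, simulated |
|---|---|---|---|---|
| 0 | 19.0 | 6.13 | 0.90 | 0.90 |
| 10 | 19.6 | 6.34 | 0.88 | 0.87 |
| 20 | 21.5 | 6.93 | 0.82 | 0.81 |
| 30 | 24.2 | 7.81 | 0.73 | 0.70 to 0.71 |

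Under no treatment effect, type I error was 0.050 to 0.055 and the mean estimate was within 0.2 points of zero.

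**Remedies, simulated across the same values of D.**
- One list plus a lead-v-subsite term: power about 0.88 to 0.89.
- One list plus terms for all four sites: about 0.87 to 0.88.
- Blocks within site plus a site term: about 0.88 to 0.90.
- Blocks within site without a site term, at D = 20: type I error 0.024 and power 0.83. Stratifying alone is conservative and recovers little power.

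**The case against.** Several objections have force.

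- **Other operators and a single list are inferences.** Section 12.6.1 does not say who operates at the subsites, and section 3.4 does not say whether lists are central or per site. Both readings are the natural ones, since sites are added to raise accrual and no stratum is named, but they remain readings.
- **The documents do not establish a between-site difference.** A reader might set the lead operator's 55 to 65% beside the published range and infer a large surgeon effect. The published range is across studies and relative to presurgical volume, while the denominator of the lead figure is not stated, so the two may not share a metric. Studies also differ in patients, technique and measurement, whereas this trial has common eligibility and one operative description. The planning study's 51% is only 4 to 14 points below the lead figure. D is therefore an assumption.
- **This is not bias.** A reader might infer a spurious BioBridge effect or an inflated false-positive rate. Averaged over randomizations the estimate is unbiased and type I error is near nominal. A 6-point shift needs both D = 20 and a 90th-percentile imbalance; the median shift is about 2 points.
- **The sentence in section 3.4 is not wrong.** Blocking does balance the arms over time, and the sentence claims nothing about site.

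What stands is that a multi-site surgical trial with 12 controls has no provision for site in either its allocation or its analysis.

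**Conclusion.** The point holds as a matter of precision and chance confounding in the single realised trial, not as systematic bias. If sites give the same VLNT result, nothing is lost. If lead site and subsites differ by 10, 20 or 30 points, power at the 20-point target falls from about 0.90 to 0.87, 0.81 and 0.70. At 20 points, the estimate shifts by about 2 points at the median imbalance and by about one standard error in the worst tenth of allocations. These figures rest on an assumed single list, an assumed 30/10/10/10 split and an assumed difference; the documents supply none of the three. The documents do not support the stronger claims that the comparison is likely to be distorted or that operators are known to differ. The change is still worth making because its main part costs almost nothing.

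**What to change.** 1. In section 12.4, add site to the primary model as a fixed effect, coded lead site v subsites if subsites are small. This alone recovers most of the lost power. It uses one degree of freedom, or three if all four sites are fitted; with no site difference the simulated power cost of the single term is about 0.01 or less.
2. In sections 3.4 and 12.1.1, state that randomization is within site at 4:1, and put this in place before subsites open, since it cannot be applied to patients already randomized. If per-site lists are already intended, say so.
3. Specify concealed central assignment and varied block sizes (multiples of 5 keep the ratio). The trial is open-label and a fixed block of 5 holds one control, so once a site has seen its control, the rest of that block is known there.

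Step 2 should not be taken without step 1, because stratified allocation without the model term is conservative.

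Remaining costs: incomplete blocks may move the total slightly from 48:12, and very small subsites may still have no control. With fixed blocks of 5 within site and subsites of about 6 patients each, some site lacked a control in 25% of simulated trials, against 65% on a single list.
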